6.1.5 Secondary Efficacy Analyses

The secondary efficacy analyses are described below. They will be summarized with means, standard deviations, medians and ranges for continuous variables and with counts and percentages for categorical variables.

The percentage of subjects who show improvement will be compared between groups using chi-square test or Fisher's exact test, as appropriate. Fisher's exact test will be used if the expected frequency in any of the cells of the crosstabulation is less than 5.

Change from baseline at Week 30 in MMSE, CDR-SOB, NPI, GDS and ADCS-ADL will be compared between groups using t-test or Kruskal-Wallis tests, as appropriate. If the change is approximately normally distributed, t-test will be used. If the change is markedly non-normally distributed, Kruskal-Wallis test will be used.

6.1.6 Exploratory Efficacy Analyses

Change from baseline scores at Visits 6, 9, 12, 13 and 14 or Early Termination for: ADAS-Cog, MMSE, CDR-Box, NPI, GDS, and ADCS-ADL will be summarized with means, standard deviations, medians and ranges by treatment group and visit. Biomarkers in blood [Amyloid beta 40, Amyloid beta 42, Amyloid precursor protein intracellular domain (AICD), soluble neuregulin-1 (sNRG-1)] will be summarized at all visits with means, standard deviations, medians and ranges for continuous variables and with counts and percentages for categorical variables.

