3.6 Study Endpoints and Variables

3.6.1 Study Endpoints

Primary endpoints used to determine the safety and efficacy of AstroStem is the following:

- Number of subjects with treatment related adverse events as assessed by analysis of adverse events including symptoms, and abnormal findings on physical examination, vital signs, ECG, and standard laboratory examination results
- Change of ADAS-Cog (Alzheimer's Disease Assessment Scale-cognitive subscale) from baseline at Week 30

The **secondary endpoints** used to determine the efficacy and safety of AstroStem are the following:

- Change of MMSE (Mini-mental status examination) from baseline at Week 30
- Changes of CDR-SOB (Clinical Dementia Rating-Sum of Boxes) from baseline at Week 30
- Changes of NPI (Neuropsychiatric Inventory) from baseline at Week 30
- Changes of GDS (Geriatric Depression Scale) from baseline at Week 30
- Change of ADCS-ADL (Alzheimer's Disease Cooperative Study Activities of Daily Living) from baseline at Week 30
- Changes of C-SSRS (Columbia Suicide Severity Rating Scale) from baseline at Week 30
- Change of MRI imaging results from baseline at Week 30
- Biomarkers in blood: Amyloid beta 40, Amyloid beta 42, Amyloid precursor protein intracellular domain (AICD), soluble neuregulin-1 (sNRG-1)

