3.6.2 Efficacy Variables

- ADAS-Cog at Visits 3, 6, 9, 12, 13 and 14 or Early Termination

- MMSE at Visits 1, 3, 6, 9, 12, 13 and 14 or Early Termination
- CDR-Box at Visits 3, 6, 9, 12, 13 and 14 or Early Termination
- NPI at Visits 3, 6, 9, 12, 13 and 14 or Early Termination
- GDS at Visits 3, 6, 9, 12, 13 and 14 or Early Termination
- ADCS-ADL at Visits 3, 6, 9, 12, 13 and 14 or Early Termination
- Biomarkers in blood [Amyloid beta 40, Amyloid beta 42, Amyloid precursor protein intracellular domain (AICD), soluble neuregulin-1 (sNRG-1)] at Visits 3, 13 and 14 or Early Termination

The rating scales used in this study are ADAS-Cog (Alzheimer's Disease Assessment Scale-cognitive subscale), MMSE (Mini-mental status examination), CDR-SOB (Clinical Dementia Rating-Sum of Box), NPI (Neuropsychiatric Inventory), GDS (Geriatric Depression Scale) and ADCS-ADL (Alzheimer's Disease Cooperative Study Activities). All questionnaires that are subject-administered should be completed by the subjects alone or along with caregiver at the beginning of each visit to minimize influences from other procedures to be performed at that visit. A short explanation should be given to each subject about the purpose and the necessity of these questionnaires.

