6.1.3 Significance Level

The primary efficacy hypothesis test will be performed using a 5% significance level. For the secondary efficacy endpoints, hypothesis tests will be performed individually at the 5% significance level. All hypothesis tests will be performed with two-sided alternative hypotheses. No adjustments on the significance level for multiple comparisons are planned, as this is a phase 1/2 study.

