Appendix 7. ADCS-ADL (Alzheimer's Disease Cooperative Study Activities of Daily Living)

Appendix 8. C-SSRS (Columbia Suicide Severity Rating Scale)

Appendix 9. Instruction for Liposuction Procedure

Appendix 10. IP Administration Instruction for Clinical Sites

Appendix 1. Laboratory Parameters

Blood and urine samples for complete laboratory evaluation (hematology, serum chemistry, biomarker analysis and urinalysis) at Visits 1, 3, 6, 9, 12, 13 and 14 or Early Termination.

HEMATOLOGY	CHEMISTRY	URINALYSIS	BIOMARKER***
Hemoglobin	Total bilirubin	Color	Amyloid beta 40
Hematocrit	Alkaline phosphatase	Appearance	Amyloid beta 42
RBC	ALT (SGPT)	Specific gravity	Amyloid
WBC	AST (SGOT)	pH	precursor protein
MCV	Blood urea nitrogen	Protein	intracellular
MCH	(BUN)	Glucose	domain (AICD)
MCHC	Creatinine	Ketones	soluble
Neutrophils (absolute)	Glucose	Bilirubin	neuregulin-1
Lymphocytes (absolute)	Albumin	Blood	(sNRG-1)
Monocytes (absolute)	Total protein	Leukocyte esterase	
Eosinophils (absolute)	Sodium	WBC	
Basophils (absolute)	Potassium	RBC	
Platelets	Chloride	Epithelial cell	
PT-INR	Bicarbonate	Bacteria	
	Calcium	Hyaline casts	
	HCG *		
	HIV **		
	HBV**		
	HCV**		
	VDRL**		

* HCG (pregnancy test) only for all females of childbearing potential at Visits 1, 3, 12, 13 and 14 or Early Termination

** Visit 1 only

*** Visits 3 and 13, 14 or Early Termination

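### Blood biomarkers are listed as secondary efficacy endpoints but analysed only descriptively as exploratory, with no planned between-arm estimate or confidence interval

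*Protocol*

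**What the plan says.** **Status.** Protocol 3.6.1 introduces its secondary list as endpoints "used to determine the efficacy and safety of AstroStem are the following", and the last entry is the four blood biomarkers; the synopsis does the same. Protocol 3.6.2, headed Efficacy Variables, lists them again with their sampling times: "soluble neuregulin-1 (sNRG-1)] at Visits 3, 13 and 14 or Early Termination". Appendix 1 confirms those times in a footnote: "Visits 3 and 13, 14 or Early Termination".

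**Testing rule.** Protocol 6.1.3: "For the secondary efficacy endpoints, hypothesis tests will be performed individually at the 5% significance level", and "All hypothesis tests will be performed with two-sided alternative hypotheses".

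**Analysis.** Protocol 6.1.5 covers five scales: "Change from baseline at Week 30 in MMSE, CDR-SOB, NPI, GDS and ADCS-ADL will be compared between groups using t-test or Kruskal-Wallis tests". Biomarkers are not mentioned there. They appear only in 6.1.6, Exploratory Efficacy Analyses, where they "will be summarized at all visits with means, standard deviations, medians and ranges for continuous variables". The sentence just before it in 6.1.6 gives the clinical scales a change from baseline; the biomarker sentence does not.

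**SAP.** Table 3 (section 2.3) places the biomarkers under exploratory efficacy, as a summary, while the scales in the same table are entered as changes. SAP 4.7.3 adds a t-test or Kruskal-Wallis test for the scales at the exploratory visits and keeps the biomarkers descriptive at baseline, Visit 13 and Visit 14 or Early Termination. SAP 4.2 excludes covariate adjustment. SAP 5 reports no departures from the protocol's analyses.

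**The concern.** One set of endpoints has two statuses. Sections 3.6.1, 3.6.2 and 6.1.3 read together make the biomarkers secondary efficacy endpoints that are tested. Sections 6.1.5 and 6.1.6 and the SAP make them exploratory quantities that are tabulated. Someone writing the study report could follow either reading after seeing the data.

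The analysis itself is also thin. Protocol section 2 cites lower Aβ and APP in a mouse model as part of the rationale, and these four analytes are the trial's only blood measures related to it. Samples are scheduled at Visit 3 and Visit 13 in the same subjects, so a paired or baseline-adjusted comparison is available without further sampling. The plan does not specify one. Routine laboratory values, vital signs and ECG all get a change from baseline (SAP 4.8.3, 4.8.5, 4.8.6), so the biomarkers receive less than safety chemistry does.

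At stake is whether the report contains a prespecified biomarker effect with its uncertainty, or only columns of means and SDs from which readers draw their own contrasts.

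**Working it through.** **1. Passages side by side**

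| Place | Status of biomarkers | Between-arm comparison at Week 30 |
|---|---|---|
| Protocol 3.6.1 and synopsis | Secondary | – |
| Protocol 3.6.2 | Efficacy variable | – |
| Protocol 6.1.3 | Reached by the general rule, not named | Test at 5%, two-sided |
| Protocol 6.1.5 | Absent | None (five scales only) |
| Protocol 6.1.6 | Exploratory | None |
| SAP Table 3 and 4.7.3 | Exploratory | None |
| SAP 5 | No change declared | – |

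That the summaries are of levels rather than changes is an inference. It rests on the contrast with the scales in the same paragraph of 6.1.6 and in SAP Table 3.

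**2. What the planned tables allow**

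SAP 4.1 gives n, mean and SD by treatment. For a subject measured at both visits, change = Week 30 value − Visit 3 value. If the same subjects contribute at both visits, the mean change equals the difference of the two visit means, so a crude between-arm difference in change can be read off. Its standard error needs

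Var(change) = s₀² + s₃₀² − 2·r·s₀·s₃₀,

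and the correlation r is not in the tables. If some subjects miss Week 30, the two visit means also cover different subjects, since nothing is imputed (Protocol 6.1.8, SAP 4.5).

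**3. Precision**

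The plan has no power or precision figure to reproduce: Protocol 6.2 predefines n = 22, 11 per group. Everything below is in units of the between-subject SD of the analysed variable, taken as equal in both arms and at both visits.

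Unadjusted Week 30 comparison:
- 95% half-width = t(0.975, 20) × √(2/11) = 2.086 × 0.426 = 0.89 SD.
- Difference detectable with 80% power (two-sided 5%, noncentral t) = 1.26 SD.
- With an assumed 9 or 8 evaluable per arm: half-width 1.00 or 1.07 SD; detectable 1.41 or 1.51 SD.

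Standard error relative to that comparison, where r is the assumed baseline to Week 30 correlation (not given in the documents):
- change score: √(2(1 − r))
- baseline-adjusted: √(1 − r²)

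| r | Change score | Baseline-adjusted | Adjusted detectable difference (1.256 × multiplier) |
|---|---|---|---|
| 0.3 | 1.18 | 0.95 | 1.20 SD |
| 0.5 | 1.00 | 0.87 | 1.09 SD |
| 0.7 | 0.77 | 0.71 | 0.90 SD |
| 0.9 | 0.45 | 0.44 | 0.55 SD |

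The adjusted multipliers ignore the one degree of freedom spent on the covariate and any chance baseline imbalance. The change score is worse than the plain Week 30 value below r = 0.5; baseline adjustment is not worse at any r in the table.

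**4. Multiplicity**

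Protocol 6.1.5 has five secondary change-score tests. If the four biomarkers were also tested at 5%, the chance of at least one false positive, assuming independent tests, would go from 1 − 0.95⁵ = 22.6% to 1 − 0.95⁹ = 37.0%.

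**The case against.** The strongest reply has four parts.

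- *The data are not hidden.* Tables are by treatment and SAP 4.1 also plans by-subject listings, from which paired changes can be worked out. This stands. A reader might infer that the plan yields no information on a biomarker effect, or could neither show nor exclude one; the documents do not support that. What is missing is a prespecified contrast with its standard error and interval. The SAP's allowance for additional exploratory analyses does not supply one, because it leaves the choice open.
- *Section 6.1.3 does not name biomarkers.* Correct, and the list in 3.6.1 mixes efficacy with safety: MRI and C-SSRS are on it and, as safety variables, are not tested (6.1.7). A reader might infer an explicit promise to test biomarkers; there is only a general rule. It still reaches them, because 3.6.2 lists them as efficacy variables while MRI and C-SSRS sit in 3.6.3 as safety variables. It is also fair that 6.1.6 and the SAP agree on method. The conflict is over status, and over the rule that goes with it.
- *The study is small and, by Protocol 6.2, not hypothesis-driven.* That argues against relying on p-values. It does not argue against an interval, and small arms make use of the baseline value more worthwhile.
- *More comparisons mean more false positives.* True, as quantified above. Reporting estimates rather than tests limits the harm.

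A reader might also infer a defect in the sampling times, since the post-baseline samples at Weeks 30 and 52 fall after dosing ends at Week 18, or in the absence of an Aβ42/Aβ40 ratio. The documents do not support either as an error. Week 30 is the efficacy time point, the footnote in Appendix 1 settles what its opening line leaves loose, and the ratio is not an endpoint anywhere. Both are design preferences.

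**Conclusion.** The point holds as an inconsistency of status together with a missing estimate. The protocol's endpoint sections and general testing rule make the biomarkers secondary efficacy endpoints; its analysis sections and the SAP treat them as exploratory summaries, and the SAP declares no change. Between-arm estimates or intervals planned for the four analytes: none in either document.

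Any such estimate will be imprecise, with a half-width of about 0.89 SD unadjusted at 11 per arm. The gain from baseline adjustment rests entirely on an assumed correlation: modest at 0.5, substantial at 0.7 to 0.9. The textual finding needs none of these assumptions. The primary ADAS-Cog analysis is unaffected.

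**What to change.** 1. Give the biomarkers one status in the synopsis, Protocol 3.6.1, 6.1.3, 6.1.5 and 6.1.6, and SAP Tables 2 and 3. If they become exploratory, record that as a change in SAP 5.
2. Whichever status is chosen, add for Aβ40, Aβ42, AICD and sNRG-1 a between-arm estimate at Week 30 adjusted for the Visit 3 value, with 95% CI. One form is a model on the log scale reported as a geometric mean ratio; the documents say nothing about the distributions, so the scale should be fixed in advance. Add change from baseline by arm at Weeks 30 and 52.
3. Amend SAP 4.2 to permit this adjustment; otherwise step 2 contradicts it.
4. State that these results are reported as estimates with intervals, without multiplicity adjustment.

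The cost is protocol and SAP wording, four more estimates and a few descriptive rows. No new visit, sample or assay is needed. The downside is four more comparisons without multiplicity adjustment. SAP 4.9 describes the interim safety look as already done, so subjects have been treated; the wording should be final before the aggregate database is unblinded.

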6.1.7 Safety Analyses

AE rates will be summarized by treatment group and overall, and will be broken down by severity, seriousness and relation to study drug. Change of MRI, C-SSRS, physical examinations, vital signs, ECG and standard laboratory results will be summarized with means, standard deviations, medians and ranges for continuous variables and with counts and percentages for categorical variables. Statistical tests are not planned for safety variables.

6.1.7.1 Interim Safety Analyses

When the first 4 subjects complete Visit 4 at Week 2, one unblinded interim safety analysis can be performed by an independent safety monitor contracted by the sponsor to evaluate the safety of

AstroStem without the suspension of subject enrollment. Change of vital signs and AEs will be evaluated.

6.1.8 Missing Data

No adjustments for missing data and no imputation methods are planned for this phase 1/2 study.

6.2 Determination of Sample Size

There was no formal sample size calculation since this is a phase 1/2 study and is not a hypothesis-driven study. The number of enrolled subjects is predefined at n=22, for 11 subjects per group.

7. SAFETY DATA COLLECTION, RECORDING, AND REPORTING

7.1 Definitions

7.1.1 Adverse Events

An adverse event is defined in the 21 CFR 312.32(a) as “Adverse event means any untoward medical occurrence associated with the use of a drug in humans, whether or not considered drug related.”

An adverse event (also referred to as an adverse experience) can be any unfavorable and unintended sign (e.g., an abnormal laboratory finding), symptom, or disease temporally associated with the use of a drug, without any judgment about causality. An adverse event can arise from any use of the drug (e.g., off-label use, use in combination with another drug) and from any route of administration, formulation, or dose, including an overdose. Worsening of a pre-existing medical condition (e.g., diabetes, migraine headaches, and gout) after the drug administration should be considered an adverse event if there is either an increase in severity, frequency, or duration of the condition or an association with significantly worse outcomes.

The investigator is responsible for reviewing laboratory test results and determining whether an abnormal value in an individual study subject represents a change from baseline values. Abnormal laboratory findings without clinical significance (based on the investigator's judgment) should not be recorded as adverse events; however, laboratory value changes requiring therapy or adjustment in prior therapy are considered adverse events.

Adverse events will be reviewed continuously throughout the study.

7.1.2 Serious Adverse Events

A serious adverse event (SAE) is any AE or suspected adverse reaction that in the view of either the investigator or Sponsor, results in any of the following outcomes:

- Death
- A life-threatening AE: it is defined as an AE or suspected adverse reaction that in the view of the investigator or Sponsor, its occurrence places the patient or subject at immediate risk of death. It does not include an AE or suspected adverse reaction that, had it occurred in a more severe form, might have caused death.
- Inpatient hospitalization or prolongation of existing hospitalization
A persistent or significant incapacity or substantial disruption of the ability to conduct normal life function.
- A congenital anomaly/birth defect

- Important medical events that may not result in death, be life-threatening, or require hospitalization may be considered serious when, based upon appropriate medical judgment, they may jeopardize the patient or subject and may require medical or surgical intervention to prevent one of outcomes listed in the above definition

Life threatening: An adverse event or suspected adverse reaction is considered “life-threatening” if, in the view of either the investigator or sponsor, its occurrence places the patient or subject at immediate risk of death. It does not include an adverse event or suspected adverse reaction that, had it occurred in a more severe form, might have caused death.

Hospitalization: Any adverse event leading to hospitalization or prolongation of hospitalization will be considered as ‘serious’, UNLESS at least one of the following exceptions is met:

- the admission results in a hospital stay of less than 24 hours OR
- the admission is pre-planned (i.e., elective or scheduled surgery arranged prior to the start of the study) OR

However, it should be noted that invasive treatment during any hospitalization may fulfill the criteria of ‘medically important’ and as such may be reportable as a SAE dependent on clinical judgment.

Disability means a substantial disruption of a person’s ability to conduct normal life functions.

Important medical event: As guidance for determination of important medical events see the ‘WHO Adverse Reaction Terminology – Critical Terms List’. These terms either see or might be indicative of a serious disease state. Such reported events warrant special attention because of their possible association with a serious disease state and may lead to more decisive action than reports on other terms.

7.2 Reporting Procedures for All Adverse Events

The investigator is responsible for ensuring that all adverse events (as defined in Section 7.1) observed by the investigator or reported by subjects after the first dose of each subject are properly captured in the subject’s medical records and reported on the eCRF.

Documentation must be supported by an entry in the subject’s file. A laboratory test abnormality considered clinically relevant, e.g., causing the subject to withdraw from the study, requiring treatment or causing apparent clinical manifestations, or judged relevant by the investigator, should be reported as an adverse event. Each event should be described in detail along with subject identification, relationship to investigational product, start and stop dates, severity, action taken, and outcome.

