3.2.1 Inclusion Criteria

- 1) Subjects who are males or females of any race, aged 50 and above at the time of signing the Informed Consent Form
- 2) Subjects who can understand and provide written informed consent (assent).
- 3) Subjects who have diagnosis of probable mild-to-moderate Alzheimer disease according to NINCDS-ADRDA (National Institute of Neurological and Communicative Disorders and Stroke; Alzheimer's Disease and Related Disorders Association) criteria
- 4) Subjects who have MMSE Score of 16 to 26
- 5) Subjects who are taking FDA-approved AD medications (donepezil, galantamine, memantine, rivastigmine or their combinations) treatment on a stable dosage for at least 3 months prior to screening.
- 6) Subjects who have one (or more) identified adult caregiver (study partner) who is able to read, understand, and speak the designated language at the study site; either lives with the subject or sees the subject for ≥ 2 hours/day ≥ 4 days/week; and agrees to accompany the subject to each study visit and to participate in the subject's clinical assessments.

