3.6.3 Safety Variables

- Hematology, blood chemistry and urinalysis at Visits 1, 3, 6, 9, 12, 13 and 14 or Early Termination. See Section Appendix 1 for a complete list of laboratory tests to be done.
- ECG evaluation at Visits 1, 3, 6, 9, 12, 13 and 14 or Early Termination
- Complete physical examination at Visits 1, 3, 6, 9, 12, 13 and 14 or Early Termination
- Vital signs (sitting blood pressure, pulse, breathing, and temperature) and weight will be measured at all visits.
- MRI Scan of the brain at Visit 1, 9, 13 and 14 or Early Termination.
- C-SSRS at Visit 3, 6, 9, 12, 13, and 14 or Early Termination
- Data regarding AEs and concomitant medications will be collected at all visits

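### Protocol 7.2 names the investigator and the subject as sources of adverse events but makes no provision for study-partner reports, so between-visit symptoms may be under-ascertained in both arms

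*Protocol*

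**What the plan says.** Protocol 7.2, which covers the reporting of all adverse events, makes the investigator responsible for events "observed by the investigator or reported by subjects after the first dose of each subject". Those are the two sources it names. It adds that a clinically relevant laboratory abnormality is to be reported as an adverse event.

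The other places that deal with collection name no source. Protocol 3.6.3 states: "Data regarding AEs and concomitant medications will be collected at all visits". The visit descriptions in 4.1.2 to 4.4 tell staff to record adverse events where applicable, without saying who is to be asked or how. SAP 4.8.1 defines and tabulates adverse events and adds no rule on sources.

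On the population, Protocol 3.2.1 admits "Subjects who have diagnosis of probable mild-to-moderate Alzheimer disease according to NINCDS-ADRDA" criteria and "Subjects who have MMSE Score of 16 to 26". The same section requires an adult caregiver who "agrees to accompany the subject to each study visit and to participate in the subject's clinical assessments".

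The first primary endpoint in Protocol 3.6.1 is the "Number of subjects with treatment related adverse events as assessed by analysis of adverse events including symptoms", together with abnormal findings on physical examination, vital signs, ECG and standard laboratory tests. Protocol 6.1.7 plans no statistical tests for safety, so the counts themselves are the result.

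**The concern.** All subjects have a disease of memory, and symptoms count towards a primary endpoint. A headache, a dizzy spell or a bad night that begins and ends between visits reaches the record only if someone remembers it and says so. Section 7.2 relies on the subject for this and does not mention the person best placed to help.

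The protocol uses the partner in this way elsewhere. The ADCS-ADL (Appendix 7) has to be an interview of the study partner, the CDR worksheet (Appendix 4) has informant questions, and the NPI (Appendix 5) is answered about the patient and carries caregiver initials. The partner is an established informant on function and behaviour, but not on safety.

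If symptoms are missed, the number of affected subjects is too low in whichever arm they occur. With 11 subjects per arm and a purely descriptive safety analysis, one or two missed subjects would change the picture. Up to three centers may take part (Protocol 3.1). Leaving it to each site whether to ask the partner could also make ascertainment differ between sites.

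**Working it through.** **Which events are exposed**

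| Route to an adverse event | Where stated | Depends on recall? |
|---|---|---|
| Physical examination, ECG, laboratory tests at Visits 1, 3, 6, 9, 12, 13, 14 | Protocol 3.6.3 | No |
| Vital signs at all visits | Protocol 3.6.3 | No |
| Clinically relevant laboratory abnormality | Protocol 7.2 | No |
| Observation during infusion and for at least 1 hour afterwards | Appendix 10 | No |
| Transient symptoms between visits | Protocol 3.6.1 (symptoms count), 7.2 | Yes |

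Only the last row is exposed. The recall interval is about 2 weeks between dosing visits (4.2.2 to 4.2.6), about 12 weeks from Visit 12 to Visit 13 (4.3.1) and about 22 weeks from Visit 13 to Visit 14 (4.3.2).

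**What can be computed**

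The documents give 11 subjects per group (Protocol 6.2) and no expected event rate, no reporting rate and no sample-size calculation. There is no figure of the plan's own to reproduce, and no under-count can be derived. What follows is an illustration on assumed values.

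Let *p* be the true proportion of subjects in an arm with a related event, and *s* the proportion of those subjects recorded as affected by any route. Then:

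- expected number recorded = 11 × *p* × *s*
- chance that none is recorded = (1 − *p* × *s*)^11

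Chance that none of 11 is recorded:

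| Assumed *p* | *s* = 100% | 90% | 75% | 50% |
|---|---|---|---|---|
| 10% | 31.4% | 35.4% | 42.4% | 56.9% |
| 20% | 8.6% | 11.3% | 16.7% | 31.4% |
| 30% | 2.0% | 3.1% | 6.1% | 16.7% |

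For example, at *p* = 20% and *s* = 75%, (1 − 0.15)^11 = 0.85^11 = 0.167. The expected number recorded at *p* = 20% is 2.20, 1.98, 1.65 and 1.10 across the four columns.

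If none of 11 is recorded, the exact one-sided 95% upper limit on the recorded risk is 1 − 0.05^(1/11) = 0.238. Dividing by *s*, treated as known, gives the limit on the true risk: 23.8%, 26.5%, 31.8% and 47.7% at *s* = 100%, 90%, 75% and 50%.

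**How to read *s***

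*s* is the overall capture per subject, not the accuracy of self-report. If half of the affected subjects could be known only through recalled symptoms, and half of those were missed, then *s* = 1 − 0.5 × 0.5 = 75%. The lowest column therefore needs a strong assumption: most related events would have to be of the recalled kind, with much of that recall failing.

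**Effect on the comparison**

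If *s* is the same in both arms, each expected count and their difference are multiplied by *s*, while the ratio of expected counts is unchanged.

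**The case against.** The strongest reply is that 7.2 describes the investigator's duty and shuts nobody out. It does not say that these are the only sources, and it does not bar partner reports. Protocol 7.1.1 defines an adverse event without regard to who reports it, 3.6.3 and the visit sections set no limit on source, and serious events in 7.3 are tied to the investigator's awareness however it arises. A partner who is in the room and takes part in assessments will often speak up, and a careful site may already ask. This stands: a reader might infer that partner-reported events are excluded, and the text does not support that. The gap is an omission.

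Much of the endpoint rests on scheduled examinations and tests, and infusions are monitored. Staff must also confirm before each repeat dose that no infusion or allergic reaction followed the previous one. This stands for measured and witnessed events. It does not cover transient symptoms at home, and the pre-dose check does not say who is to be asked. The two longest intervals fall after the last dose, which lowers the stakes there, but every dosing interval is still exposed.

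The illustration rests on assumed values. It also gives each subject a single capture probability, although a subject with several events has several chances to be counted. This stands too: low values of *s* probably overstate the loss per subject.

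A reader might also infer a bias in favour of AstroStem. Nothing in the documents supports that. The arms are equal in size, the trial is designed as double-blind, and the partner requirement applies to every subject.

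**Conclusion.** The point holds as a weakness of ascertainment. Section 7.2 names two sources, no other section adds the partner, and the subjects' disease makes unaided recall of symptoms doubtful. Symptom events between visits may be under-ascertained in both arms. Events found by examination, vital signs, ECG, laboratory tests or infusion monitoring are not affected.

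A reader might go further and conclude that the primary safety endpoint is under-counted. The documents do not show this. They contain no reporting-completeness figure and nothing that tests self-report at an MMSE of 16 to 26. The SAP's statement in 4.9 that no adverse events were reported among the first four subjects is no evidence either way. Nor is the partner's presence at every visit assured: the criterion records an agreement at entry, and no rule covers a missed attendance.

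The size is therefore unknown. On the assumptions above, capture of 75% would raise the upper limit after 0 of 11 from 23.8% to 31.8%, and at a true risk of 20% it would raise the chance of recording no affected subject from 8.6% to 16.7%. That is enough to justify a cheap change, but not to call the safety result invalid.

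**What to change.** Amend Protocol 7.2 so that it covers events observed by the investigator or reported by either the subject or the study partner. In the visit sections, require one open, non-leading question about adverse events, put in the same words to both at every visit, including Visits 13 and 14 and Early Termination. Recording on the eCRF who reported each event is optional. It would let the report show how much the partner added.

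The cost is a sentence in 7.2, a standard question in the visit procedures and a few minutes per visit with someone who has already agreed to attend. Somewhat more adverse events will be recorded. Because of the blinding, the increase should be similar in both arms. The descriptive analyses in SAP 4.8 need no change.
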